5.5.2 Duration of seizure-free period

The duration of the seizure-free period will be measured from the first day the participant reports no seizures of at least 28 consecutive days until the last day reported without seizures during the Treatment Period. Missing daily seizure counts will be treated as non-zero reports, without any value assigned. This statistic will be provided for each participant.

The endpoint will be included on the listing related to participants seizures; listed on the RS and by randomized treatment arm.

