### **6.5           Concomitant medication(s)/treatment(s)**

#### **6.5.1        Permitted concomitant treatments (medications and therapies)**

Investigator should take utmost precaution for the dosage of concomitant medications for study participants who might have impaired renal function (GFR 30ml/min/1.73m^2 to 45ml/min/1.73m^2) and should refer to the prescribing information for potential dose adjustment.

Given that study participants will be administered steroids up to Week 12 of the study, it is up to the discretion of investigator to initiate prophylaxis for pneumocystis carinii pneumonia if deemed appropriate.

The following concomitant medications are permitted during the study:

- Antiepileptic drugs: all study participants should preferably continue to take their Baseline AED regimen unchanged over the whole study period. Decreases in daily dose or discontinuation of AEDs are permitted, per investigator assessment. However, initiation of new AEDs or dose increase of a AED are not allowed.
- Corticosteroids (only as specified in the protocol)
- Topical steroids: the use of topical or local is permitted
- Antipsychotics: the dose should be stable within 1 week of the cognitive assessments
- Benzodiazepines may be used if at stable daily dosage regimen as concomitant medication. However, per needed benzodiazepine treatment that is deemed medically necessary in the opinion of the investigator should be administered, and the study participant's continuation in the study must be discussed between the medical monitor and the investigator.

Administration of COVID-19 vaccines will be recorded in the concomitant medication eCRF page. The specific name of the vaccine and the exact date of administration should be recorded, as instructed in the completion guideline. See Section 8.3.9 for details.

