### 9.3.3.3 Duration of seizure-free period

The duration of the seizure-free period will be measured from the first day the participant reports no seizures for at least 28 consecutive days until the last day without seizures during the Treatment Period. The endpoint will be descriptively summarized on the RS with respect to the randomized treatment arm and stratification factors (see Section 6.3).

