5.1.1.2 End date of the Treatment Period

The end date of the Treatment Period will be either the date of EOT visit (Week 25) for participants completing the Treatment Period, or the date of the early discontinuation (EDisc) visit for participants who discontinued during the Treatment Period. If a subject does not have an EOT/EDisc visit, then either the date of the last scheduled or unscheduled visit during the Treatment Period or the date of last known dose of IMP during the Treatment Period, whichever is later, will define the end date of the Treatment Period.

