5.1.1.3 Study periods

The maximum study duration per study participant is 38 weeks. There are 3 study periods:

- Screening Period: up to 42 days;
- Treatment Period: 24 weeks;
- Safety Follow-Up Period: 8 weeks.

The following definitions for starting and entering the study periods will be applied:

- **Screening Period** starts at the time of the informed consent date and ends the day before the first dose administration of IMP (i.e. generally the day before Day 1 visit date).
- **Treatment Period** starts on the day of first dose administration of IMP (Day 1) and ends at EOT visit or at EDisc visit for participants withdrawn from the study before Week 24 visit. Participants who are withdrawn from the study during the Treatment Period should complete the assessments outlined for the EOT/EDisc visit and enter the SFU Period.
- **Safety Follow-Up Period** starts with one day after Treatment Period and ends at the final assessments at the EOS visit. Participants who have a completed status in the study termination CRF are considered to have completed the Treatment and SFU Period (i.e. entire study).

Notes:

- The end of the study is defined as the date of the last visit of the last participant in the study.
- Patients should be dosed within 2 days of being randomized.

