5.3 Primary Endpoint Analysis

5.3.1 Definition of endpoint

Participants who reported no seizures for 28 consecutive days and maintained the seizure count as zero until the end of Treatment Period will be treated as meeting the primary endpoint.

For the purpose of deriving the primary efficacy endpoint, any intermittent missing diary

seizure count recording will not be imputed but considered as non-zero for the purposes of the primary endpoint.

A by-participant listing of daily seizure count will be provided, including seizure freedom, time to first occurrence of seizure freedom, time to seizure freedom, and duration of seizure freedom.

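### The seizure-free duration ends on the last seizure-free day of treatment rather than at the first seizure after the qualifying run, so intervening seizure days can be counted as seizure-free time

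*SAP*

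**What the plan says.** SAP 5.5.2 defines the duration as "measured from the first day the participant reports no seizures of at least 28 consecutive days" and ends it "until the last day reported without seizures during the Treatment Period". On missing diary days it adds: "Missing daily seizure counts will be treated as non-zero reports, without any value assigned". Protocol 9.3.3.3 has the same start and ends the period "until the last day without seizures during the Treatment Period". Neither section says that a seizure after the qualifying run ends the period, that the days between the two boundaries must be seizure-free, or that seizure days are deducted.

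The primary endpoint is worded differently. SAP 5.3.1 requires that the participant reached 28 seizure-free days and "maintained the seizure count as zero until the end of Treatment Period will be treated as meeting the primary endpoint".

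The protocol planned a descriptive summary of the duration by arm and stratification factor. The SAP, written after recruitment stopped at 12 participants (SAP section 3), reduces this to one value per participant on the seizure listing. SAP 5.3.1 puts that value in the same listing as the daily seizure counts.

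**The concern.** A seizure-free period should contain no seizures. Here both ends are fixed without regard to what happens between them. A programmer following the text would code last seizure-free day minus first day of the run plus one, and any relapse before the last seizure-free day would be counted as seizure-free time.

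The pattern that triggers this is plausible in this trial. Protocol 6.5.1 notes that "study participants will be administered steroids up to Week 12 of the study", so a participant may be seizure-free early under steroid cover and have seizures again as the dose falls. Protocol 7.1.3 takes some of these participants off study drug, but a recurrence that meets none of its criteria can continue on treatment. For such a participant the listed duration could equal or exceed that of someone who never relapsed.

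**Working it through.** The documents give no figure for this endpoint, so there is nothing to reproduce. The check applies the written rule to constructed diaries. The diary patterns are assumptions, chosen to show the range.

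**Inputs**
- Length of treatment: "Treatment Period: 24 weeks" (SAP, Study periods), taken as 24 × 7 = 168 days. The end date is formally the end-of-treatment visit, so the bound below moves by any days that visit falls after Day 168.
- End of treatment after early discontinuation: "the date of the early discontinuation (EDisc) visit for participants who discontinued during the Treatment Period" (SAP, End date of the Treatment Period).
- A missing day counts as not seizure-free (SAP 5.5.2).
- The clock is assumed to start no earlier than Day 1.

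**Formulas.** Let S be the first day of the first run of at least 28 seizure-free days, R the last day of that unbroken run, and L the last seizure-free day in the Treatment Period.
- Written rule: L − S + 1
- Unbroken run: R − S + 1
- Overstatement: L − R

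| Constructed diary | S | R | L | Written rule | Unbroken run | Overstatement | Seizure or missing days counted |
|---|---|---|---|---|---|---|---|
| A. Free 15-168 | 15 | 168 | 168 | 154 | 154 | 0 | 0 |
| B. Free 1-28, seizures 29-167, free 168 | 1 | 28 | 168 | 168 | 28 | 140 | 139 |
| C. Free 15-42, seizures 43-98, free 99-168 | 15 | 42 | 168 | 154 | 28 | 126 | 56 |
| D. Free 15-42, then seizures on 6 of every 7 days to 168 | 15 | 42 | 168 | 154 | 28 | 126 | 108 |
| E. Free 15-42, seizures every day 43-168 | 15 | 42 | 42 | 28 | 28 | 0 | 0 |
| F. Free 15-42, seizures 43-55, free 56, early discontinuation visit on 56 | 15 | 42 | 56 | 42 | 28 | 14 | 13 |
| G. Free 15-74, diary missing 75, free 76-168 | 15 | 74 | 168 | 154 | 60 | 94 | 1 |

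**Reading the table**
- The bound is the largest L minus the smallest R: 168 − 28 = 140 days, reached only in a case such as B.
- B, with 139 seizure days, scores 168. A, with no relapse, scores 154. The rule can therefore rank two participants in the wrong order.
- C and D get the same value as A, although 56 and 108 of the counted days had seizures. In C, 70 of the 126 extra days (99-168) are seizure-free but belong to a second run.
- E shows that the error needs at least one seizure-free day after the relapse begins. F shows the cap at early discontinuation.
- The condition in E is easily met by a participant who stays on treatment. If each of the 126 remaining days were seizure-free independently with probability 0.01, the chance of at least one such day is 1 − 0.99^126 = 0.72. With probability 0.05 it is 1 − 0.95^126 = 0.998. Both probabilities and the independence are assumptions.

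**The case against.** The strongest reply is that the name of the quantity implies one unbroken run, so this is loose wording. That may well be the intent, but the written end point does not say it. The missing-data sentence classes a missing day as non-zero without saying that a non-zero day ends the period, and where the authors wanted continuity, as in the primary endpoint, they wrote it.

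Several stronger readings are tempting, and the documents do not support them.
- A reader might infer that the value hides the sustained effect beyond steroids that the trial looks for. It does not. The primary endpoint measures sustained freedom and scores a relapser as not meeting it, and the relapse is visible in the daily counts on the same listing.
- A reader might infer that the whole of any relapse is always credited. It is credited only up to the last later seizure-free day, and not at all in case E.
- A reader might infer that only a clinically meaningful recurrence needing a change in therapy leads to discontinuation. Protocol 7.1.3 also lists lack of seizure improvement, mRS criteria and a confirmed RBANS decline. A relapse as long as that in case B, with the participant still on study drug, is therefore an extreme.
- A reader might infer that every participant starts study drug on high-dose steroids. The synopsis and Protocol 4.1 allow randomization during a taper, down to 40 mg/day.

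The limited use of the value also stands as an objection to its weight. It is exploratory, is not a listed endpoint in Protocol section 3 or SAP 1.1, and is neither summarized by arm nor tested in the SAP.

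**Conclusion.** The rule as written is wrong, not merely under-specified: followed literally, it can list 168 days for a 28-day run. The overstatement ranges from 0 to 140 days per participant, with 140 an upper bound that assumes a 168-day Treatment Period and a clock starting on Day 1. How many of the 12 participants have a diary that triggers it cannot be known from the documents.

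The consequence is small. It is confined to one exploratory value on a per-participant listing, where a careful reader could detect the error from the adjacent daily counts. No primary or secondary result depends on it. It is worth correcting because that listing is the only planned output for this quantity and the correction is cheap.

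**What to change.** In SAP 5.5.2, end the period on the day before the first non-zero or missing diary day after the start of the first qualifying run, or at the end of the Treatment Period if there is no such day. State explicitly that a missing day ends the run because it counts as non-zero. Record the departure from Protocol 9.3.3.3 in SAP 6.7, which currently lists no changes to protocol-planned analyses. Under this rule cases B to F each give 28 days and case A stays at 154.

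Listing any later runs of at least 28 days is optional. Reporting the longest run instead of the first would be a preference that departs from the first-run anchor in both documents.

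The cost is one sentence, one entry in SAP 6.7 and one changed derivation, with no new data. The small downside is that a single missed diary day shortens the reported duration: case G falls from 154 to 60 days. A footnote on the listing marking runs ended by a missing entry would let readers tell these from relapses.

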5.5.3 Change in RBANS domains

The individual RBANS domain index scores (immediate memory, visuospatial/constructional, delayed memory, language, and attention) will be calculated per RBANS US v2.0 (13Nov2019) (see [Section 6.2](#)).

The observed Baseline and post-Baseline individual RBANS domain index scores at each scheduled visit will be descriptively summarized on the RS by treatment group, together with the change from Baseline. All scores will be listed for each participant; produced by randomized treatment arm.

5.5.4 Short Form 36-item (SF-36)

By-participant listings of the SF-36 V2 questionnaire responses only, SF-36 V2 will be provided by treatment group. Domains and component scores will not be calculated.

5.5.5 Euro-Quality of Life 5-Dimensions, 5 Levels (EQ-5D-5L)

The EQ-5D-5L essentially consists of 2 pages: the EQ-5D descriptive system and the EQ visual analogue scale (VAS).

A by-participant listing will be produced using the RS to summarize answers provided to each of the 5 dimensions of the EQ-5D descriptive system at each scheduled visit for each participant by treatment group.

5.5.6 Clinical Global Impression of Severity (CGI-S)

The CGI-S is a clinician reported outcome that requires the clinician to assess how much the patient's illness has improved or worsened relative to a baseline state at the beginning of the intervention.

A frequency table will be produced using the RS to summarize answers provided to the CGI-S ("none," "mild," "moderate," "severe", "very severe") at each scheduled visit by treatment group

A by-participant listing of CGI-S will be provided.

If any other data is available on PGI-S, PGI-C for any participants this will be listed.

5.6 Safety Analyses

All safety analyses will be presented using the RS unless RS and SS are different and then SS will be used. Listings will be presented by treatment group, participant, and stratification factors (time from the disease onset and RBANS score, see [Section 5.1.1.8](#)); tabulations will be presented by treatment group . Unless otherwise specified, safety analyses will be presented by safety treatment group as defined in [Section 4.3](#).

5.6.1 Extent of Exposure

The following summaries will be generated using descriptive statistics based on the SS:

- a) Study IMP duration (day) calculated as follow:

Study IMP duration (day) = Date of last dose – Date of first dose + 1

If data cut-off is applied and date of last dose > date of cut off, date of last dose will be replaced by the cut-off date in the above formula.

- b) Cumulative study IMP Duration using > 0 weeks, \geq 4 weeks, \geq 8 weeks, \geq 12 weeks, \geq 16 weeks, \geq 20 weeks, and 24 weeks;
- c) Number of Infusions Received as continuous and using the following categorical values: 1-4, 5-8, 9-12, 13-16, 17-20, and 21-24;

All drug administration details will be listed.

5.6.2 Adverse Events

5.6.2.1 Data considerations

Adverse events will be recorded from the time of informed consent until study completion. All AEs will be coded (see [Section 5.1.1.5](#)).

In addition, AEs will be classified according to the Common Terminology Criteria for Adverse Events (CTCAE) Version 5 or later for severity. For any AEs where it is not possible to provide a CTCAE grading, the events will be assessed using a standard intensity classification (mild, moderate and severe). For the purpose of the tabulations all CTCAE severity classifications will be mapped to a mild/moderate/severe grade as described below:

Grade: Intensity

- Grade 1 - Mild
- Grade 2 - Moderate
- Grade 3, 4, 5- Severe

These will be tabulated together with the AEs that were not classified according to CTCAE criteria i.e., all Grade 1 AEs as per CTCAE criteria will be included in the ‘mild’ category together with those AEs classified as mild as per the ‘standard’ intensity classification. In the case a mapped standard intensity classification per above rule is different from the standard intensity classification on CRF, the worst case will be used as the standard intensity classification (i.e., an AE with Grade 1 and moderate as intensity classification will be classified into moderate).

Any AE that occurred during the study will be defined as “**any AE**”.

A TEAE is defined as an AE starting on or after the time of first administration of IMP or any unresolved event already present before the first administration of IMP that worsens in intensity following exposure to treatment up to the end of the Treatment Period and including the 8-week (56 days) SFU. Adverse events starting before the date of the first administration of IMP or after SFU will not be considered TEAEs. Such events will be listed only.

Where dates are missing or partially missing, AEs will be assumed to be treatment-emergent unless evidence exists that does not allow the AE to be treatment-emergent. Handling of missing dates for classification of AEs as TEAEs is described in [Section 6.1.7.1.2](#).

The following rules will be used to assign a TEAE to a study period:

- **Treatment Period:** a TEAE will be assigned to the Treatment Period for the tabulations if the start date of the event is on or after the date of the first administration of IMP on Day 1, up to 7 days following the final dose of IMP;
- **SFU Period:** a TEAE will be assigned to the SFU Period for the tabulations if the start date of the event is greater than 7 days after the date of the final dose of IMP until 8 weeks following the final dose; events starting later than 8 weeks (56 days) following the final dose of IMP are not considered TEAEs.

In the case of early withdrawal in the Treatment Period, a TEAE will be assigned to the Treatment Period based on the last received IMP plus 168 hours (7 days). Subsequent TEAEs (up to 8 weeks (56 days) post-last dose) will be assigned to the SFU Period.

A TEAE will be counted as a TEAE related to IMP if the response to the question “Relationship to Study Medication” is “Related”. Severe TEAEs are those with CTCAE Grade 3 or above, or those without a CTCAE grading classified as ‘severe’ by the Investigator.

AEs will be presented as “number of participants (percentage of participants) [number of events]”. In this style of output, “[number of events]” will include all cases of an AE including repeat occurrences in individual participants, while “number of participants” will count each participant only once.

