### Assessment of Intensity

The investigator will make an assessment of intensity for each AE and SAE reported during the study and assign it to 1 of the following categories:

- Mild: An event that is easily tolerated by the participant, causing minimal discomfort and not interfering with everyday activities.
- Moderate: An event that causes sufficient discomfort and interferes with normal everyday activities.
- Severe: An event that prevents normal everyday activities. An AE that is assessed as severe should not be confused with a SAE. Severe is a category utilized for rating the intensity of an event; and both AEs and SAEs can be assessed as severe.
- An event is defined as ‘serious’ when it meets at least 1 of the predefined outcomes as described in the definition of an SAE, NOT when it is rated as severe (eg, a severe AE may be either serious or not serious, depending on whether these criteria are also met).

The National Cancer Institute Common Terminology Criteria for Adverse Events (NCI-CTCAE) should be used as a supportive standardization instrument to evaluate AEs and SAEs but the final intensity grading by the investigator must be mild, moderate, or severe.

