5.6.2.2 Adverse events summaries

The number and percentage of participants who experience AEs will be summarized by treatment group. The following outputs will be created:

- Incidence of TEAEs (defined as the number and percentage of participants with at least one TEAE (incidence proportion) – Overview. The following categories will be included by treatment arm:
 - Any TEAEs
 - Serious TEAEs
 - Participant discontinuation due to TEAEs (defined as TEAEs with “Did the Adverse Event Lead to Dropout ticked” as “Yes”)
 - Permanent withdrawal of IMP due to TEAEs (defined as TEAEs with an action taken with study medication of “drug permanently withdrawn”)
 - Temporary withdrawal of IMP due to TEAEs (defined as TEAEs with an action taken with study medication of “drug temporarily interrupted”)
 - Treatment-related TEAEs
 - Severe TEAEs

All Deaths (AEs leading to death). Note: Above TEAEs will be summarized to capture the overall and by MedDRA Primary SOC (PSOC), Higher level term (HLT) and PT. Additionally, the frequency of TEAEs will be summarized by MedDRA PSOC and PT.

- The number, percentage of participants and frequency of the following TEAEs will be summarized by SOC, HLT and PT for:
 - Incidence of any TEAEs
 - Incidence of Serious TEAEs
 - Incidence of Permanent withdrawal of IMP due to TEAEs
 - Incidence of Any TEAEs by Maximum Intensity (mild, moderate and severe) Incidence of Any TEAEs by Relationship
 - Incidence of Any TEAEs by Event Outcome
 - Incidence of any TEAE's per 100 Patient years.

AESIs are the cases of potential Hy's Law (see [Section 6.1.9](#)).

AESMs or AESIs will be identified based on the assessment by the Investigator as recorded in the CRF. An AE will be counted as an AESMs or AESIs if there is a 'yes' response to the question "Adverse Event of Special Interest or Event of Special Monitoring?" and not otherwise. These flags will be included in the listings.

When applicable, adverse event summaries will be ordered by alphabetical SOC, alphabetical HLT within SOC and decreasing frequency of PT in the rozanolixizumab total column for tables.

Listings of all AEs, permanent withdrawal of IMP due to AEs, participant discontinuation from study due to AEs, and AEs leading to death will be presented by treatment group.

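### SAP 5.6.2.1 classes a TEAE with CTCAE Grade 1 or 2 and CRF intensity severe in two ways, so the Severe TEAEs overview row can fall below the maximum-intensity table

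*SAP*

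**What the plan says.** SAP section 5.6.2.1 (Data considerations) sets out AE severity in steps.

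- AEs are graded by CTCAE, with a fallback: "For any AEs where it is not possible to provide a CTCAE grading, the events will be assessed using a standard intensity classification" of mild, moderate or severe.
- "For the purpose of the tabulations all CTCAE severity classifications will be mapped to a mild/moderate/severe grade as described below". Grade 1 maps to mild, Grade 2 to moderate, and Grades 3 to 5 to severe.
- If the mapped grade and the intensity on the CRF differ, "the worst case will be used as the standard intensity classification". The SAP's own example is that "an AE with Grade 1 and moderate as intensity classification will be classified into moderate".
- Later in the same section: "Severe TEAEs are those with CTCAE Grade 3 or above, or those without a CTCAE grading classified as" severe by the investigator.

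SAP section 5.6.2.2 then plans two outputs that depend on severity. One is a Severe TEAEs row in the TEAE overview. The other is "Incidence of Any TEAEs by Maximum Intensity (mild, moderate and severe"), by system organ class, high level term and preferred term.

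In the protocol, Appendix 3 (Assessment of Intensity) asks the investigator to rate the intensity of every AE and SAE. It gives CTCAE a supporting role and says that "the final intensity grading by the investigator must be mild, moderate, or severe".

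**The concern.** The worst-case rule lets the CRF intensity raise an event above its CTCAE grade. The later definition of severe TEAEs lets the investigator's rating of severe count only when there is no CTCAE grade. An event with a low CTCAE grade and a CRF rating of severe is therefore severe under one sentence and not severe under the other.

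The definition names severe TEAEs, so a programmer would naturally apply it to the overview row of that name and apply the worst-case intensity to the maximum-intensity table. One report could then give two different numbers of participants with a severe TEAE in the same arm, with no stated rule to say which is right. The overview row is the figure most readers look at first, and it would be the lower one.

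**Working it through.** The SAP gives no figure to reproduce here. The check applies both rules to every possible combination of gradings.

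**Inputs.** CTCAE grade is none, 1, 2, 3, 4 or 5. CRF intensity is mild, moderate or severe. That gives 6 × 3 = 18 combinations. The mapping and both rules come from SAP 5.6.2.1.

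**Worst-case rule.** Final intensity = the worse of (mapped CTCAE grade, CRF intensity), or the CRF intensity alone if there is no grade. The event is severe if the result is severe.

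**Severe-TEAE definition.** The event is severe if the CTCAE grade is 3 or above, or if there is no grade and the CRF intensity is severe.

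| CTCAE grade | CRF intensity | Worst-case rule | Severe-TEAE definition |
|---|---|---|---|
| None | Severe | Severe | Severe |
| None | Mild or moderate | Not severe | Not severe |
| 1 | Severe | **Severe** | **Not severe** |
| 2 | Severe | **Severe** | **Not severe** |
| 1 or 2 | Mild or moderate | Not severe | Not severe |
| 3, 4 or 5 | Any | Severe | Severe |

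**Counts of severe combinations.**
- Worst-case rule: 1 (no grade) + 2 (Grades 1 and 2 with CRF severe) + 3 × 3 (Grades 3 to 5) = 12.
- Severe-TEAE definition: 1 + 0 + 9 = 10.
- The rules disagree on 12 − 10 = 2 combinations and agree on the other 16. These are counts of logical cases, not frequencies of events.

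**Direction.** Every combination that is severe under the definition is also severe under the worst-case rule. If the definition feeds the overview and the worst-case rule feeds the intensity table, the overview count is at most equal to the severe count in the intensity table.

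**Size.** Both outputs count a participant once. The overall participant count differs only if a discordant event occurs in someone who has no TEAE that both rules call severe. SAP section 3 gives 12 randomized participants but not the split by arm. Assuming 6 per arm, one such participant is 1/6 = 16.7 percentage points. A 5 and 7 split would give 1/5 = 20.0 or 1/7 = 14.3 points. If no discordant event occurred, the difference is zero.

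**After the fix.** With one rule in both outputs, the discordant combinations fall from 2 of 18 to 0.

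**The case against.** Four points can be made on the other side.

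1. **Both gradings may never coexist.** SAP 5.6.2.1 introduces the mild/moderate/severe scale for events that cannot be given a CTCAE grade. Read strictly, no event has both, and the two rules never meet. This does not stand: the worst-case rule and its Grade 1 example are pointless unless both can be present and differ, and Protocol Appendix 3 requires an investigator intensity for every AE. The objection does suggest that a Grade 1 or 2 event rated severe should be uncommon, since investigators rate intensity with CTCAE as support.

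2. **The link from rule to table is inferred.** The mapping is stated to be for the tabulations, and the overview is also a tabulation. Section 5.6.2.2 assigns neither rule to a table. This stands in part: the defect is conflicting wording, not two outputs already shown to disagree. But if the worst-case rule is meant to govern both outputs, the later definition contradicts it and should not be there.

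3. **The change log says most AE summaries were removed.** The current text of section 5.6.2.2 keeps both outputs, so the conflict is live.

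4. **The consequence is small.** AE outputs are descriptive and all AEs are listed, so with 12 participants a mismatch could be traced to single events. This stands, and it limits the weight of the point.

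A reader might also infer more than the documents support.

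- *That the later definition breaches the protocol by overriding the investigator's final grade.* Protocol Appendix 3 does not say how discordant grades are to be tabulated. The worst-case rule overrides the investigator too: Grade 3 with CRF moderate becomes severe. The argument does not favor one rule over the other.
- *That severe headaches could be missed.* Protocol Appendix 13 ties headache severity to CTCAE version 5.0, and SAP 5.6.2.2 identifies events of special monitoring from a CRF question. Neither severity rule affects that identification.

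**Conclusion.** SAP 5.6.2.1 is inconsistent as written, but only for TEAEs with CTCAE Grade 1 or 2 and a CRF intensity of severe. It would be wrong to conclude that every event the investigator calls severe is affected: those with no CTCAE grade, or with Grade 3 or above, are classed alike under both rules.

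The possible error runs one way, toward a lower count in the Severe TEAEs overview row. Its size rests on three conditions: that such an event occurred, which the documents do not show; that the participant had no other severe TEAE; and, for the figure of about 17 percentage points, an assumed 6 participants per arm. The planned total of 68 is not a useful base for the size, because recruitment ended with 12 randomized.

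This is a minor reporting inconsistency that is worth correcting because the correction is specific and cheap. It does not bear on any efficacy conclusion.

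**What to change.** In SAP 5.6.2.1, replace the sentence that defines severe TEAEs with: severe TEAEs are those whose final intensity, after the worst-case rule above, is severe. State that this derived intensity is used for both the Severe TEAEs overview row and the maximum-intensity table.

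Applying the narrower definition in both places would also remove the conflict. The worst-case rule is the better choice because the SAP already sets it out for discordant grades, and it never discards a rating of severe from either source.

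The cost is one SAP sentence and one derived variable shared by the two outputs. No new data are needed. The severe count in the overview may rise slightly; all other events keep their classification.
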